 - Patients on stable dose of a β -blocker or calcium channel antagonist for pre-existing baseline conditions (e.g., hypertension) may be permitted if resting heart is \geq 50 bpm.
 - History of angina pectoris, symptomatic pericarditis, myocardial infarction, or any cardiac arrhythmias (e.g., ventricular, supraventricular, nodal arrhythmias, or conduction abnormality) within 12 months prior to study entry
 - History of documented congestive heart failure (New York Heart Association Class II–IV) or cardiomyopathy
 - Left ventricular ejection fraction < 50% as determined by multiple-gated acquisition scan or echocardiogram
 - QT interval corrected through use of Fridericia's formula (QTcF) > 470 ms based on mean value of triplicate ECGs, history of long or short QT syndrome, Brugada syndrome or known history of corrected QT interval prolongation, or torsades de pointes
 - History or presence of an abnormal ECG that is clinically significant in the investigator's opinion, including complete left bundle branch block, second- or third-degree heart block, sick sinus syndrome, or evidence of prior myocardial infarction
 - History of ventricular dysrhythmias or risk factors for ventricular dysrhythmias such as structural heart disease (e.g., severe left ventricular systolic dysfunction, left ventricular hypertrophy), coronary heart disease (symptomatic or with ischemia demonstrated by diagnostic testing), clinically significant electrolyte abnormalities (e.g., hypokalemia, hypomagnesemia, hypocalcemia), or family history of long QT syndrome
- Current treatment with medications that are well known to prolong the QT interval
- Active inflammatory bowel disease or chronic diarrhea, short bowel syndrome, or major upper gastrointestinal surgery including gastric resection
- Treatment with strong CYP3A4 inhibitors or inducers within 14 days or 5 drug elimination half-lives (whichever is longer) prior to randomization

- Known HIV infection
- Serious infection requiring oral or IV antibiotics, or other clinically significant infection within 14 days prior to screening
 - Patients who fully recovered from serious and clinically significant infections within 14 days prior to screening are eligible.
- Any serious medical condition or abnormality in clinical laboratory tests that, in the investigator's judgment, precludes the patient's safe participation in and completion of the study

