- History of documented hemorrhagic diathesis, coagulopathy, or thromboembolism
- Active cardiac disease or history of cardiac dysfunction including any of the following:
 - History or presence of symptomatic bradycardia or resting heart rate < 50 bpm at screening

Patients on stable dose of a β -blocker or calcium channel antagonist for pre-existing baseline conditions (e.g., hypertension) may be permitted if resting heart is ≥ 50 bpm.
 - History of angina pectoris, symptomatic pericarditis, myocardial infarction, or any cardiac arrhythmias (e.g., ventricular, supraventricular, nodal arrhythmias, or conduction abnormality) within 12 months prior to study entry
 - History of documented congestive heart failure (New York Heart Association Class II–IV) or cardiomyopathy
 - Left ventricular ejection fraction $< 50\%$ as determined by multiple-gated acquisition scan or echocardiogram
 - QT interval corrected through use of Fridericia's formula (QTcF) > 470 ms based on mean value of triplicate ECGs, history of long or short QT syndrome, Brugada syndrome or known history of corrected QT interval prolongation, or torsades de pointes

- History or presence of an abnormal ECG that is clinically significant in the investigator's opinion, including complete left bundle branch block, second- or third-degree heart block, sick sinus syndrome, or evidence of prior myocardial infarction
- History of ventricular dysrhythmias or risk factors for ventricular dysrhythmias such as structural heart disease (e.g., severe left ventricular systolic dysfunction, left ventricular hypertrophy), coronary heart disease (symptomatic or with ischemia demonstrated by diagnostic testing), clinically significant electrolyte abnormalities (e.g., hypokalemia, hypomagnesemia, hypocalcemia), or family history of long QT syndrome
- Current treatment with medications that are well known to prolong the QT interval (see Section 4.4.2.2)
- Active inflammatory bowel disease or chronic diarrhea, short bowel syndrome, or major upper gastrointestinal (GI) surgery including gastric resection
- Treatment with strong CYP3A4 inhibitors or inducers within 14 days or 5 drug elimination half-lives (whichever is longer) prior to randomization
- Known HIV infection
- Serious infection requiring oral or IV antibiotics, or other clinically significant infection within 14 days prior to screening

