4.5.12 Laboratory, Biomarker, and Other Biological Samples

Laboratory samples should be collected according to the schedule of activities (see [Appendix 1](#) and [Appendix 2](#)). Results of the following assessments should be available for review at each clinic visit (as required per the schedule of activities) prior to dosing to inform dosing decisions: complete blood count with differential, total bilirubin, ALP, AST, ALT, creatinine, and BUN/urea.

Samples for the following laboratory tests will be sent to the study site's local laboratory for analysis:

- Hematology: WBC count, RBC count, hemoglobin, hematocrit, platelet count, and differential count (neutrophils, eosinophils, basophils, monocytes, lymphocytes, and other cells)
- Chemistry panel (serum or plasma): sodium, potassium, chloride, glucose, BUN or urea, creatinine, total protein, albumin, phosphate, calcium, total and direct bilirubin, ALP, ALT, AST, urate, and LDH
- Fasting lipid panel: cholesterol, HDL, LDL, and triglycerides
- Coagulation: INR, aPTT, and PT
- Urinalysis, including dipstick (pH, specific gravity, glucose, protein, ketones, and blood) and microscopic examination (sediment, RBCs, WBCs, casts, crystals, epithelial cells, and bacteria)

- HBV serology: HBsAg, HBcAb, and (if HBsAg test is negative and total HBcAb test is positive) HBV DNA
 - If a patient has a negative HBsAg test and a positive total HBcAb test at screening, an HBV DNA test must also be performed to determine if the patient has an HBV infection.
- HCV serology: HCV antibody and (if HCV antibody test is positive) HCV RNA
 - If a patient has a positive HCV antibody test at screening, an HCV RNA test must also be performed to determine if the patient has an HCV infection.
- FSH, for patients <60 years
- Estradiol, for patients <60 years

The following samples will be sent to one or several central laboratories or to the Sponsor or a designee for analysis (see [Appendix 2](#)), unless otherwise indicated:

- Plasma samples for PK analysis
- Blood and plasma samples for exploratory research on biomarkers and biomarker assay development
- Archival (diagnostic) or newly collected tissue sample obtained prior to initiation of treatment for determination of baseline Ki67 scores and for exploratory research on biomarkers and biomarker assay development (see [Section 4.5.10](#) for tumor tissue sample requirements)

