4.5.13 Electrocardiograms

Single ECG recordings will be obtained at specified timepoints, as outlined in the schedule of activities (see Appendix 1), and may be obtained at unscheduled timepoints as indicated.

All ECG recordings must be performed using a standard high-quality, high-fidelity digital electrocardiograph machine equipped with computer-based interval measurements. Lead placement should be as consistent as possible. Twelve-lead single ECG recordings must be performed after the patient has been resting in a supine position for at least 10 minutes. All ECGs are to be obtained prior to other procedures scheduled at that same time (e.g., vital sign measurements, blood draws). Circumstances that may induce changes in heart rate, including environmental distractions (e.g., television, radio, conversation) should be avoided during the pre-ECG resting period and during ECG recording.

For safety monitoring purposes, the investigator must review, sign, and date all ECG tracings. Paper copies of ECG tracings will be kept as part of the patient's permanent study file at the site. The following should be recorded in the appropriate eCRF: heart rate, RR interval, QRS interval, PR duration, uncorrected QT interval, and QTcF based on the machine readings of the individual ECG tracings. Any morphologic waveform changes or other ECG abnormalities must be documented on the eCRF. If considered appropriate by the Sponsor, ECGs may be analyzed retrospectively at a central laboratory.

If at a particular post-dose timepoint the mean QTcF is >500 ms and/or >60 ms longer than the baseline value, another ECG must be recorded, ideally within the next 5 minutes, and ECG monitoring should continue until QTcF has stabilized on two successive ECGs. The Medical Monitor should be notified. Standard-of-care treatment may be instituted per the discretion of the investigator. If a PK sample is not scheduled for that timepoint, an unscheduled PK sample should be obtained. A decision on study drug discontinuation should be made, as described in Section 5.1.4. The investigator should also evaluate the patient for potential concurrent risk factors (e.g., electrolyte abnormalities, co-medications known to prolong the QT interval, severe bradycardia).

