Appendix 1: Schedule of Activities

CTSQ=Cancer Therapy Satisfaction Questionnaire; D=day; ECOG=Eastern Cooperative Oncology Group; FSH=follicle-stimulating hormone; PK=pharmacokinetic; PO=oral; PRO=patient-reported outcome; PRO-CTCAE=Patient-Reported Outcomes Common Terminology Criteria for Adverse Events; QD=once a day.

Notes: On treatment days that coincide with clinic visits, all assessments should be performed prior to dosing unless otherwise specified.

- ^a Results of standard-of-care tests or examinations performed prior to obtaining informed consent and within 28 days prior to Day 1 may be used; such tests do not need to be repeated for screening, unless otherwise indicated.
- ^b Patients will receive either GDC-9545 30 mg PO QD or anastrozole 1 mg PO QD for 2 weeks.
- ^c Patients will receive GDC-9545 30 mg PO QD (Days 1–28/cycle) plus palbociclib 125 mg PO QD (Days 1–21/cycle) or anastrozole 1 mg PO QD (Days 1–21/cycle) plus palbociclib 125 mg PO QD (Days 1–21/cycle) for four cycles (16 weeks), for 28 days per cycle. Starting with Day 1 of Cycle 1, and on Day 1 of each 28-day cycle thereafter, study treatment will be administered in the clinic, after the study assessments.
- ^d Surgery will be performed within 14 days after the final treatment in the neoadjuvant treatment phase. If surgery is delayed, if the patient is not operable or will not undergo surgery for other reasons, or does not complete 16 weeks (four cycles) of combination therapy, an optional biopsy may be performed as a separate procedure within 2 days from the end of the combination treatment (see [Appendix 2](#)).
- ^e Patients who complete the study or who discontinue the study prematurely will return to the clinic for an end of study visit 28 (\pm 3) days after the final study treatment.
- ^f A fresh post-dose biopsy will be obtained on Day 15 (+ 1 day). Blood will be collected from the patient, along with additional samples (see [Section 4.5.10](#) and [4.5.12](#)).
- ^g Informed consent must be documented before any study-specific screening procedure is performed, and may be obtained more than 28 days before initiation of study treatment.
- ^h Questionnaires will be self-administered before the patient receives any information on disease status, prior to the performance of non-PRO assessments, and prior to the administration of study treatment (see [Section 4.5.14](#)).

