Appendix 1: Schedule of Activities

- ⁿ Patients should be resting in a supine position for at least 10 minutes prior to ECG recording. All ECGs will be obtained prior to other procedures scheduled at that same time (e.g., vital sign measurements, blood draws).
- ^o Hematology includes WBC count, RBC count, hemoglobin, hematocrit, platelet count, and differential count (neutrophils, eosinophils, basophils, monocytes, lymphocytes, and other cells).
- ^p Chemistry panel (serum or plasma) includes, sodium, potassium, chloride, glucose, BUN or urea, creatinine, total protein, albumin, phosphate, calcium, total and direct bilirubin, ALP, ALT, AST, urate, and LDH.
- ^q Fasting lipid panel will assess cholesterol, HDL, LDL, and triglycerides (after ≥ 8 hours of fasting).
- ^r Only for patients < 60 years.
- ^s Urinalysis includes dipstick (pH, specific gravity, glucose, protein, ketones, and blood) and microscopic examination (sediment, RBCs, WBCs, casts, crystals, epithelial cells, and bacteria). Urinalysis should be performed as clinically indicated during study treatment.
- ^t Patients will receive a medication diary and should be instructed to complete the medication diary each day immediately after taking their all study medication during each cycle (e.g., Cycles 0–4). The medication diary and unused capsules or tablets in their bottles should be collected and reviewed on Day 1 of each cycle for drug accountability.
- ^u For sample biopsy details, refer to [Appendix 2](#) and [Section 4.5.10](#).
- ^v Ultrasound should be performed at screening (within 28 days prior to randomization), between Day 21 of Cycle 4 of the neoadjuvant treatment phase and surgery, and as clinically indicated.
- ^w See [Section 4.5.11](#).
- ^x Medication (e.g., prescription drugs, over-the-counter drugs, vaccines, herbal or homeopathic remedies, nutritional supplements) used by a patient in addition to protocol-mandated treatment from 7 days prior to initiation of study drug until end of study visit.

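### Hypomagnesemia is named as an excluding abnormality, but no scheduled screening test measures magnesium

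*Combined protocol and SAP*

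**What the plan says.** The exclusion appears in the same words in the Synopsis and in Section 4.1.2. It covers a history of ventricular dysrhythmias or risk factors for them, and one group of risk factors is "clinically significant electrolyte abnormalities (e.g., hypokalemia, hypomagnesemia, hypocalcemia), or family history of long QT syndrome". The electrolytes are examples, and no numeric threshold is attached to any of them.

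Section 4.5.12 defines the chemistry panel, run at the site's local laboratory, as "Chemistry panel (serum or plasma): sodium, potassium, chloride, glucose, BUN or urea, creatinine, total protein, albumin, phosphate, calcium", followed by "total and direct bilirubin, ALP, ALT, AST, urate, and LDH". Appendix 1 footnote p repeats the list: "Chemistry panel (serum or plasma) includes, sodium, potassium, chloride, glucose, BUN or urea, creatinine, total protein, albumin, phosphate, calcium", with the same remaining items. Appendix 1 schedules the panel at screening and at later visits.

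Two other provisions bear on the point. Appendix 1 footnote a allows earlier results to count: "Results of standard-of-care tests or examinations performed prior to obtaining informed consent and within 28 days prior to Day 1 may be used". Section 4.5.13 covers the response to a marked QTcF prolongation on treatment and includes this: "The investigator should also evaluate the patient for potential concurrent risk factors (e.g., electrolyte abnormalities".

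**The concern.** The exclusion names three electrolyte disturbances side by side, and the scheduled blood work can reveal only two of them. A site that follows the schedule exactly will measure potassium and calcium in every patient it screens and will have no magnesium value unless one exists from routine care.

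Patient safety is what is at stake. The protocol treats low magnesium as a reason to keep a patient out because of arrhythmia risk. Whether an unrecognised case is found before the first dose then depends on local habit at approximately 90 sites. Rhythm is not a remote concern here: bradycardia is a listed potential risk of GDC-9545 (Section 5.1.1.4), and bradycardia of Grade 2 or higher is an adverse event of special interest (Section 5.2.3). A baseline magnesium would also help in reading a later QTcF excursion, although Section 4.5.13 does not ask for one.

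**Working it through.** There is no power or error-rate calculation to reproduce. The check sets the criterion against the laboratory lists and the schedule.

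**1. Electrolytes named against analytes measured.** The panel in Section 4.5.12 contains sodium, potassium, chloride, glucose, BUN or urea, creatinine, total protein, albumin, phosphate, calcium, total bilirubin, direct bilirubin, ALP, ALT, AST, urate and LDH, which makes 17 analytes. Footnote p gives the same list.

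| Named in the exclusion | On the chemistry panel |
|---|---|
| Hypokalemia | Yes (potassium) |
| Hypocalcemia | Yes (calcium) |
| Hypomagnesemia | No |

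Two of three are covered.

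**2. Other scheduled tests.** Hematology, fasting lipids, coagulation, urinalysis, viral serology, FSH and estradiol are the other local laboratory tests in Section 4.5.12. None includes magnesium. In the protocol, hypomagnesemia is named only in the two copies of the exclusion.

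**3. Timing.** The chemistry row of Appendix 1, read across its 11 columns:

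| Column | Chemistry |
|---|---|
| Screening | x |
| Cycle 0 Day 1 | blank |
| Cycle 0 Day 15 | blank |
| Cycle 1 Day 1 | x |
| Cycle 1 Day 15 | x |
| Cycle 2 Day 1 | x |
| Cycle 2 Day 15 | x |
| Cycle 3 Day 1 | x |
| Cycle 4 Day 1 | x |
| Surgery | x |
| End of study | x |

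That is 9 panels, and only the screening panel precedes the first dose.

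**4. Does the protocol say that no test is intended?** In the same exclusion list it does so for other conditions. It states that HIV, HBV and HCV assessments are not required at screening if they have not been done before, and it limits the HIV exclusion to known infection. Hypomagnesemia carries neither qualifier.

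**5. Size of a remedy.**
- Screening only: 215 enrolled × 1 = 215 results, plus one for each screen failure tested (number not given).
- All panels: 215 × 9 = 1,935 results, an upper value that assumes every patient completes every visit.

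**The case against.** The strongest reply is that the criterion was never meant to depend on an assay. It is a bullet about history and risk factors, the electrolytes are illustrations, and neighbouring items such as family history of long QT syndrome have no mandated test. The exclusion for LVEF below 50% has no scheduled measurement either. The viral-infection criteria show that the protocol will exclude on known disease without testing everyone. Section 4.5.1 asks for screening evaluations to be completed and reviewed, and does not require an assay for every named example.

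Much of this stands. Section 4.5.1 is not breached, and the text does not show that universal magnesium testing was intended. The viral-infection example points the other way, however, because there the protocol says openly that testing is not required, and here it does not.

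The second reply is that the risk is already small. Entry is barred for QTcF above 470 ms, for a clinically significant abnormal ECG and for current QT-prolonging medication. Chronic diarrhea, inflammatory bowel disease, short bowel syndrome and major upper gastrointestinal surgery are also excluded. A second ECG is scheduled on Cycle 0 Day 1, and assessments precede dosing. The potential-risk list for GDC-9545 has no heading for QT prolongation or ventricular arrhythmia. Investigators may order magnesium themselves or use the general laboratory-abnormality exclusions. These points keep the matter minor, but none of these safeguards measures magnesium.

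The third reply is that, without a threshold, exclusion would still vary by site. That is true of the judgement on the result. The measurement itself would no longer vary.

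**Conclusion.** The concern holds, as a minor safety point at the low end of what should be changed. Two of the three electrolytes named in the exclusion are measured at screening and magnesium is not. Before the first dose, hypomagnesemia that is not already known is found only where a site tests on its own initiative. Known hypomagnesemia can still be excluded.

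The omission is certain from the text. Its clinical weight is not quantified: the documents give no frequency of unrecognised, clinically significant hypomagnesemia, so no number of affected patients is offered. The conclusion rests on the panel being as listed in Section 4.5.12 and footnote p. Nothing in the primary endpoint, power or analysis is affected.

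**What to change.** Add *magnesium (screening only)* to the chemistry panel in Section 4.5.12 and in Appendix 1 footnote p. The restriction needs to be written in, because footnote p defines the panel for all 9 timepoints. Run it at the local laboratory on the blood already drawn. Judge the result under the criterion's existing standard of clinical significance, so that no new threshold or management rule is needed. Accept a standard-of-care value from the 28 days before Day 1, as footnote a already allows.

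The cost is a one-line amendment in two places and one extra result per screened patient: about 215 for enrolled patients plus screen failures, fewer where an existing result is reused. There may be a few more screen failures. Testing at all 9 panels is not proposed.

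If the sponsor prefers not to test, the example can be reworded to *known hypomagnesemia*. That aligns the criterion with the schedule at no testing cost, but unrecognised cases would stay undetected, so the single screening result is the better choice.

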1. BACKGROUND

1.1 BACKGROUND ON HORMONE-RECEPTOR POSITIVE BREAST CANCER

Breast cancer is the most commonly diagnosed cancer in women, with an estimated global incidence of 2,088,849 new cases and 626,679 deaths reported in 2018 (Bray et al. 2018; IARC 2018). Approximately 80% of all breast cancers express the estrogen receptor (ER), and the vast majority of these are dependent on ER for tumor growth and progression. Modulation of estrogen activity and/or synthesis is the mainstay of therapeutic approaches in women with ER-positive breast cancer. The selective estrogen-receptor modulator, tamoxifen, and aromatase inhibitors (AIs) represent the cornerstone treatment for patients who are hormone receptor positive.

Selective ER downregulators (SERDs) have the potential to block endocrine-dependent and endocrine-independent ER signaling by ablation of ER and have been recognized to offer a therapeutic approach to ER-positive breast cancer in metastatic breast. Fulvestrant, the first generation SERD, binds, blocks, and degrades the ER, leading to complete inhibition of estrogen signaling through the ER. Fulvestrant has shown benefit over an AI (anastrozole) in frontline patients (Robertson et al. 2016; see Section 1.5.1). However, fulvestrant is hampered by intramuscular administration due to its poor physicochemical and pharmacokinetic (PK) properties.

GDC-9545, a second-generation SERD, is a novel, potent, orally bioavailable, small molecule therapeutic agent currently being developed for the treatment of patients with ER-positive breast cancer.

Tamoxifen and AI therapy are associated with significant side effects that often lead to early discontinuation of treatment. Maximizing therapeutic benefit, while minimizing treatment related toxicities, is particularly important in hormone receptor (HR)-positive, HER2-negative early breast cancer (EBC) where treatment duration is usually for 5 years or more. Currently, only approximately 60% of patients manage to complete 5 years of adjuvant endocrine therapy (Hagen et al. 2019). Improved treatment options may decrease or eliminate the risk of recurrences after adjuvant therapy and provide more tolerable treatment options (see Section 1.5.3).

